### **2.2. Secondary Objectives**

The secondary objectives are the following:

- To evaluate the persistence of the immune response to mRNA-1273 vaccine (25, 50, and 100 µg)
- To evaluate the incidence of SARS-CoV-2 infection after vaccination with mRNA-1273 or placebo
- To evaluate the incidence of asymptomatic SARS-CoV-2 infection after vaccination with mRNA-1273 or placebo

- To evaluate the incidence of COVID-19 after vaccination with mRNA-1273 or placebo. COVID-19 is defined as clinical symptoms consistent with COVID-19 AND positive RT-PCR for SARS-CoV-2

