#### **Analysis Periods**

The following analysis periods and treatment groups will be used for efficacy analyses for Part 2, the blinded phase, unless specified otherwise:

| Part 2 Group | Description  | Part 2 Blinded Phase Analysis Period for Efficacy  |
|---------------------|---|---|
| mRNA-1273           | Participants randomized to mRNA-1273 in the Blinded Phase | From randomization to the earliest date of unblinding (date on Participant Decision Visit / Crossover Day 1 or unblinding day) inclusive, |
| Placebo             | Participants randomized to Placebo in the Blinded Phase   |   |

|  |  |  |
|--|--|--|
|  |  | study discontinuation, study completion, death, and data cutoff date |
|--|--|--|

Immunogenicity data at Day 57 are analyzed regardless of participant unblinding status at Day 57. The analysis period for efficacy specified above will not be applied to immunogenicity analysis. Since immunogenicity samples are handled and tested in a blinded manner and lab testing results are objective which are not impacted by unblinding status in individual participants. Therefore, the immunogenicity data at Day 57 after participant unblinding can still be included for the Day 57 immunogenicity analysis.

The following analysis period and treatment groups will be used for safety analysis for Part 2, the blinded phase, unless specified otherwise:

| Part 2 Group | Description   | Part 2 Blinded Phase Analysis Period for Safety  |
|--------------|---|--|
| mRNA-1273    | Participants received at least one dose of mRNA-1273 in the Blinded Phase | From the date of 1 st injection to the earliest date of unblinding (date on Participant Decision Visit / Crossover Day 1 or unblinding day) exclusive, study discontinuation, study completion, death, and data cutoff date |
| Placebo      | Participants only received Placebo in the Blinded Phase                   | From the date of 1 st injection to the earliest date of unblinding (date on Participant Decision Visit / Crossover Day 1 or unblinding day) exclusive, study discontinuation, study completion, death, and data cutoff date |

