#### **2.2.3. Secondary Objective**

The secondary objective is to evaluate the persistence of the immune response to mRNA-1273 vaccine.

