## **5.3. Per-protocol (PP) Immunogenicity Subset**

### Per-protocol (PP) Immunogenicity Subset (Long-term Analysis)

Per-Protocol (PP) Immunogenicity Subset (Long-term Analysis) at Day 1, Day 57 and Day 209 consists of all participants in Immunogenicity Subset (Long-term Analysis) who meet all the following criteria:

- a) Received planned doses of study vaccination per schedule
- b) Complied with the timing of second dose of injection
- c) If participants have a diagnosis of HIV, they are not receiving highly active anti-retroviral therapy (HAART)
- d) Had a negative SARS-CoV-2 status at baseline (pre-dose 1 of mRNA-1273)
- e) Had no major protocol deviations that impact key or critical data

The PP Immunogenicity Subset (Long-term Analysis) will serve as the population for the long-term analysis of immunogenicity data.

Per-protocol (PP) Immunogenicity Subset (Part 3, First Two Doses of Primary Series)

Per-Protocol (PP) Immunogenicity Subset consists of all participants in Part 3 Immunogenicity Subset who meet all the following criteria:

- a) Received planned doses of IP per schedule
- b) Complied with the immunogenicity window based on 2nd dose injection timing
- c) If participants have a diagnosis of HIV, they are not receiving highly active anti-retroviral therapy (HAART)
- d) Had baseline (Day 1) and Day 57 Ab assessment for the analysis endpoint
- e) Had no major protocol deviations that impact key or critical data

The PP Immunogenicity Subset will serve as the primary population for the analysis of immunogenicity data in this study unless specified otherwise. Participants will be analyzed according to the treatment group for the treatment which they actually received in Part 3.

Per-protocol (PP) Immunogenicity Subset (Booster/Third Dose Analysis)

Per-Protocol (PP) Immunogenicity Subset consists of all participants in Immunogenicity Subset for Booster/Third Dose Analysis who meet all the following criteria:

For mRNA-1273 Booster Dose:

- a) Received 2 doses of planned doses of mRNA-1273 vaccination in Part 1 open-label phase or Part 2 blinded phase per schedule
- b) Received booster dose in Booster Dose Analysis

- c) If participants have a diagnosis of HIV, they are not receiving highly active anti-retroviral therapy (HAART)
- d) Had a negative SAS-CoV-2 status at baseline (pre-dose 1 of mRNA-1273 )
- e) Had BD-Day 29 Ab assessment for the analysis endpoint
- f) Had no major protocol deviations that impact key or critical data

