- g) Not receive off-study COVID-19 vaccination prior to BD-Day 29 visit

For mRNA-1273 Third Dose:

- a) Received first 2 doses of planned doses of mRNA-1273 vaccination in Part 3 open-label phase per schedule
- b) Received third dose in Third Dose Analysis
- c) If participants have a diagnosis of HIV, they are not receiving highly active anti-retroviral therapy (HAART)
- d) Had BD-Day 29 Ab assessment for the analysis endpoint
- e) Had no major protocol deviations that impact key or critical data
- f) Not receive off-study COVID-19 vaccination prior to BD-Day 29 visit

The PP Immunogenicity Subset for Booster/Third Dose analysis will serve as a population for the analysis of immunogenicity in booster/third dose by pre-booster SARS-CoV-2 status (negative vs. positive).

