### **Analysis periods**

The following analysis periods and treatment groups will be used for long-term and booster dose analysis.

- Long-term Analysis (Part 1 Open-Label Phase plus Part 2 Blinded and Open-Label Phase, until Booster Dose)

| Group               | Category                    | Start Date                      | End Date  |
|---------------------|-----------------------------|---------------------------------|---|
| mRNA-1273           | Safety                      | Date of First Dose of mRNA-1273 | Earliest date of booster dose (exclusive), study discontinuation, study completion, death, or data cutoff |
| Placebo - mRNA-1273 |                             |                                 | Earliest date of booster dose (inclusive), study discontinuation, study completion, death, or data cutoff |
| mRNA-1273           | Efficacy/
Immunogenicity | Date of First Dose of mRNA-1273 | Earliest date of booster dose (inclusive), study discontinuation, study completion, death, or data cutoff |
| Placebo - mRNA-1273 |                             |                                 | Earliest date of booster dose (inclusive), study discontinuation, study completion, death, or data cutoff |

- Long-term analysis (Part 1 Open-Label Phase plus Part 2 Blinded and Open-Label Phase, Regardless of Booster Dose) incidence rate will also be performed for the entire study period after the first dose of mRNA-1273 regardlesss of booster dose.

| Group               | Category                    | Start Date                      | End Date  |
|---------------------|-----------------------------|---------------------------------|---|
| mRNA-1273           | Safety                      | Date of First Dose of mRNA-1273 | Earliest date of study discontinuation, study completion, death, or data cutoff |
| Placebo - mRNA-1273 |                             |                                 | Earliest date of study discontinuation, study completion, death, or data cutoff |
| mRNA-1273           | Efficacy/
Immunogenicity | Date of First Dose of mRNA-1273 | Earliest date of study discontinuation, study completion, death, or data cutoff |
| Placebo - mRNA-1273 |                             |                                 | Earliest date of study discontinuation, study completion, death, or data cutoff |

- Part 3, First Two Doses of Primary Series Analysis

| Group           | Category | Start Date                      | End Date  |

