## **6.4. Immunogenicity Analysis**

The analyses of immunogenicity in long-term analysis at Day 1, Day 57, Day 209 and Day 394 (as applicable) will be based on the PP Immunogenicity Subset (Long-term Analysis) and Immunogenicity Subset (Long-term Analysis).

The analyses of immunogenicity in mRNA-1273 booster/third dose analysis will be based on

- PP Immunogenicity Subset with Pre-booster SARS-CoV-2 Negative for booster dose Analysis.

- PP Immunogenicity Subset (including Pre-booster/third dose SARS-CoV-2 Negative and Positive) for booster/third dose Analysis.

The PP Immunogenicity Subset with pre-booster SARS-CoV-2 negative will be used in the primary and secondary immunogenicity analyses for Part 1 and Part 2 booster dose analysis (Not applicable for Part 3 third dose analysis). And PP Immunogenicity Subset will be used for Part 3 third dose analysis, unless otherwise specified. The PP Immunogenicity Subset will be used in the immunogenicity analyses by pre-booster/third dose SARS-CoV-2 status (negative vs. positive).

The GMT and geometric mean (GM) level will be calculated using the following formula:

$$10^{\left\{ \frac{\sum_{i=1}^n \log_{10}(t_i)}{n} \right\}}$$

where  $t_1, t_2, \dots, t_n$  are  $n$  observed immunogenicity values or levels.

The geometric mean fold-rise (GMFR) measures the changes in immunogenicity values or levels within subjects. The GMFR will be calculated using the following formula:

$$10^{\left\{ \frac{\sum_{i=1}^n \log_{10}\left(\frac{v_{ij}}{v_{ik}}\right)}{n} \right\}} = 10^{\left\{ \frac{\sum_{i=1}^n \log_{10}(v_{ij}) - \log_{10}(v_{ik})}{n} \right\}}$$

where, for  $n$  subjects,  $v_{ij}$  and  $v_{ik}$  are observed immunogenicity values for subject  $i$  at time points  $j$  and  $k$ ,  $j \neq k$

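### The persistence titres at Day 209 and Day 394 are screened for infection only before Dose 1, so later infection or off-study vaccination can make waning look slower, and no planned analysis separates the two

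*SAP*

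**What the plan says.** The document holds two plans: one for the Part 1 open-label and Part 2 blinded phases (the first SAP), and one for the Part 2 open-label phase, booster doses and Part 3 (the second SAP).

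- **Objective.** Second SAP, Section 2.2.3: "The secondary objective is to evaluate the persistence of the immune response to mRNA-1273 vaccine". The first SAP has the same secondary objective in Section 2.2, and its Section 3.2 makes geometric means at Day 209 and Day 394 secondary endpoints.
- **Population.** Second SAP, Section 5.3: "The PP Immunogenicity Subset (Long-term Analysis) will serve as the population for the long-term analysis of immunogenicity data". Its five criteria are planned doses, second-dose timing, HIV therapy, pre-Dose 1 status ("Had a negative SARS-CoV-2 status at baseline (pre-dose 1 of mRNA-1273") and no major deviation.
- **Time points.** Sections 5.2 and 5.3 define the long-term sets at Day 1, Day 57 and Day 209. Day 394 comes in only through Section 6.4: "The analyses of immunogenicity in long-term analysis at Day 1, Day 57, Day 209 and Day 394 (as applicable").
- **Follow-up.** In the until-booster table of Section 6.1, the immunogenicity period ends at "Earliest date of booster dose (inclusive), study discontinuation, study completion, death, or data cutoff". Infection and off-study vaccination are not listed.
- **Contrast.** The mRNA-1273 booster and third-dose per-protocol sets add "Not receive off-study COVID-19 vaccination prior to BD-Day 29 visit" as a criterion separate from the deviation criterion. The primary booster set (Section 5.4) requires no evidence of infection up to BD-Day 1.

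**The concern.** Persistence means how the response to the vaccine holds up over time. A SARS-CoV-2 infection or an extra COVID-19 vaccine is a fresh antigen exposure that raises neutralizing and spike-binding antibody. Either can occur at any time between Day 57 and Day 394, so the affected share can only grow from one visit to the next. The bias therefore runs one way: it lifts the later geometric means more than the earlier ones and flattens the curve. The result then depends partly on how much virus circulated and how many families sought vaccine elsewhere. The second SAP expects such infections, since Section 6.5 derives their dates and counts them during long-term follow-up, but it does not use those dates when titres are summarised.

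**Working it through.** The plan states no figure for this analysis, so the main check is textual.

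**1. Is there any route by which a Day 209 or Day 394 titre drawn after an event is removed or shown separately?**

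| Place (second SAP unless noted) | Later infection | Off-study COVID-19 vaccine |
|---|---|---|
| 5.2 Immunogenicity Subset, long-term | Not removed; baseline status need only be available | Not removed |
| 5.3 PP subset, long-term | Not removed; pre-Dose 1 status only | Only if the deviation rules cover it |
| 6.1 until-booster period | No stop | No stop |
| 6.1 subgroups | Baseline or pre-booster/third-dose status, not status at the draw | None |
| 6.2.6 deviation rules | Not naturally a deviation | To be written before database lock |
| First SAP, 5.5 PP subset | Baseline only | Only if the deviation rules cover it |

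For infection the answer is no. For off-study vaccination it is open, but the booster and third-dose sets list that vaccination apart from major deviations, which suggests that the deviation criterion was not meant to cover it.

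**2. How large could the effect be?** Let a share p of samples be drawn after an event that multiplies the titre by k. The mean log titre rises by p × ln k, so the geometric mean is multiplied by k^p. Both p and k are assumptions.

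| p | k = 4: inflation | True 4-fold decline reads as | k = 10: inflation | True 4-fold decline reads as |
|---|---|---|---|---|
| 10% | 1.15 | 3.48 | 1.26 | 3.18 |
| 20% | 1.32 | 3.03 | 1.58 | 2.52 |
| 30% | 1.52 | 2.64 | 2.00 | 2.00 |
| 50% | 2.00 | 2.00 | 3.16 | 1.26 |

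The apparent decline is 4 / k^p. This takes the Day 57 value as unaffected.

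**3. How does that compare with sampling error?** The first SAP assumes an SD of 1.5 for ln titre (Section 4.2). As a check on that input, a 1.5-fold margin, 90% power and two-sided 5% alpha give 2 × (1.5 / ln 1.5)² × (1.960 + 1.282)² ≈ 288 per group, and 289 per group gives power 0.901. Both agree with the plan's 289 and 90%.

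Part 2 Cohort B (Day 209) and Cohort C (Day 394) each plan 132 mRNA-1273 recipients per age group (first SAP, Table 2). The 95% CI factor for one geometric mean is exp(1.96 × 1.5 / √132) = 1.29. With the plan's 25% loss to the per-protocol set, n = 99 and the factor is 1.34. Inflation exceeds 1.29 once p passes ln 1.29 / ln k: about 18% for k = 4 and 11% for k = 10. Carrying the SD of 1.5 to the later visits is an assumption, and pooling Part 1 children would narrow the interval.

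**The case against.** **The analysis is descriptive.** Section 2.1 of the second SAP says so for the Part 2 open-label phase, and no margin or success rule is attached to Day 209 or Day 394. Titres reported whatever happened after vaccination are a legitimate quantity. This stands: a reader might infer that the analyses cannot show durability at all, and that goes too far.

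**Infected children are not wholly hidden.** The first SAP allows descriptive summaries of immunologic endpoints in infected participants (6.8.1) and plans listings of their antibody values (6.8.2). The second SAP reports pre-booster geometric means (6.4.4) and analyses by pre-booster infection status (6.4). This stands in part. The summaries are optional, listings estimate nothing, and the pre-booster values cover only children who took the mRNA-1273 booster.

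**Off-study vaccination may be a major deviation.** Possibly; Section 6.2.6 leaves the rules open. It cannot be said outright that those titres are kept.

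**The first SAP.** A reader might infer from "The analysis period for efficacy specified above will not be applied to immunogenicity analysis" that its Day 209 and Day 394 titres have no stop at crossover or booster. The text does not support that. The sentence sits in a paragraph about Day 57 samples after unblinding, long-term and booster analyses are sent to the second SAP, and the until-booster period there stops at the booster. Crossover is offered only to placebo recipients, so it cannot contaminate the original mRNA-1273 arm.

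**Excluding infected children has its own bias.** It conditions on a post-vaccination event. If weaker responders are infected more often (an assumption), the remaining geometric mean is too high. This stands, and is the reason to report both analyses rather than replace one with the other.

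**Conclusion.** The point holds in limited form. Titres drawn after a breakthrough infection are kept at Day 209 and, through Section 6.4, at Day 394; those drawn after an off-study vaccine are kept unless the future deviation rules remove them. No planned analysis separates vaccine durability from later antigen exposure. The direction is towards slower apparent waning. The size is unknown from the document: 1.15- to 3.16-fold inflation under the assumed p of 10% to 50% and k of 4 to 10, and beyond the sampling error of a 132-sample geometric mean from about p = 11% to 18%, depending on k. It affects a descriptive secondary objective and leaves the Day 57 noninferiority tests untouched, so it is worth correcting without being fatal to the study.

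**What to change.** 1. At Day 209 and Day 394, pre-specify an added persistence analysis that excludes samples taken on or after the first of: a post-Dose 1 positive RT-PCR or nucleocapsid-positive result (including one from the same visit), an off-study COVID-19 vaccination, or a study booster.
2. Keep the pre-dose BD-Day 1 sample, which Table 2 of the first SAP already allows to stand in for Day 209 or Day 394.
3. In the placebo-crossover group, count from the first mRNA-1273 dose, so that the crossover doses are not themselves a reason for exclusion.
4. Report this beside the present all-samples analysis, with the number excluded at each visit and by reason.
5. Reconcile the time points in Sections 5.2 and 5.3 (to Day 209) with Section 6.4 (to Day 394).
6. If the rule is extended to BD-Day 181 and BD-Day 366, apply it only to infection or off-study vaccination after the booster; otherwise every sample at those visits would be dropped.

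**Cost.** For Day 209 and Day 394: SAP wording and a per-sample flag. Nasal swabs are scheduled at both visits and the safety calls ask about nonstudy vaccinations. Nucleocapsid testing at those visits is stated for Part 1 (first SAP, 6.4.1); its use in Part 2 should be confirmed. Ascertainment is weaker later: surveillance ended in October 2022, and the mRNA-1273 booster schedule has no swab at BD-Day 366. The statistical price is fewer late samples and the possible selection noted above.

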#### **5.4. Per-protocol (PP) Immunogenicity Subset - Pre-booster SARS-CoV-2 Negative (Booster Dose Analysis)**

PP Immunogenicity Subset - Pre-booster SARS-CoV-2 Negative (PP Immunogenicity Subset – Neg) for booster dose analysis consists of participants who are in PP Immunogenicity Subset (Booster Dose Analysis), and are pre-booster SARS-CoV-2 negative, defined as no virologic or serologic evidence of SARS-CoV-2 infection on or before BD-Day 1 (pre-booster), i.e. RT-PCR result is not positive if available at BD-Day 1 and a negative bAb specific to SARS-CoV-2 nucleocapsid on or before BD-Day 1.

PP Immunogenicity Subset - Pre-booster SARS-CoV-2 Negative for Booster Dose Analysis will serve as the population for the primary and secondary analysis of immunogenicity data in booster phase.

## 5.5. Modified Intent-to-Treat-1 (mITT1) Set

### mITT1 Set (Part 2, Cross-Over Subjects)

mITT1 Set (Part 2 Cross-Over Subjects) for placebo-mRNA-1273 group consists of all cross-over participants who were previously included in the mITT1 set for the Part 2 blinded phase analysis and in the FAS (Part 2, Cross-Over Subjects) who had no serologic or virologic evidence of prior SARS-CoV-2 infection (no positive RT-PCR test and no positive serology test based on bAb specific to SARS-CoV-2 nucleocapsid) on or before the date of the first cross-over mRNA-1273 dose in open-label phase and received at least one dose of mRNA-1273 without wrong treatment, i.e., all FAS cross-over participants excluding those with positive or missing RT-PCR test or serology test prior to the first dose of mRNA-1273 and those who received the wrong treatment in open-label phase (i.e., at least one dose received in open-label phase is not as assigned).

### mITT1 Set (Long-term Analysis)

The mITT1 Set (Long-term Analysis) consists of mITT1 Set (Part 2, Cross-Over Subjects) for Placebo-mRNA-1273 group and mITT1 Set for mRNA-1273 group. The mITT1 Set for mRNA-1273 group is same as the mITT1 Set in Part 1 open-label phase and Part 2 blinded phase.

### mITT1 Set (Booster Dose Analysis)

The mITT1 Set for booster dose analysis consists of all participants in the FAS for booster dose who had no serologic or virologic evidence of prior SARS-CoV-2 infection (both negative RT-PCR test for SARS-CoV-2 and negative serology test based on bAb specific to SARS-CoV-2 nucleocapsid) pre-booster dose and received one booster dose without wrong treatment, i.e., all FAS participants excluding those with pre-booster positive or missing RT-PCR test or serology test and those who received the wrong booster dose (i.e., dose received in booster dose is not as assigned).

Participants will be analyzed according to their treatment group (mRNA-1273-mRNA-1273 Booster or Placebo-mRNA-1273-mRNA-1273 Booster for booster dose analysis)

## 5.6. Solicited Safety Set

### Solicited Safety Set (Part 3, First Two Doses of Primary Series)

The Solicited Safety Set consists of all participants in the safety set who contribute any solicited AR data, i.e., have at least one post-baseline solicited safety assessment. The

Solicited Safety Set will be used for the analyses of solicited ARs and participants will be included in the vaccination group corresponding to the study injection they actually received. In addition, the following Solicited Safety Set is defined for each injection separately.

The First (Second) Injection Solicited Safety Set consists of all subjects in the Solicited Safety Set who have received the first (second) study injection and have contributed any solicited AR data from the time of first (second) study injection through the following 6 days. Participants will be analyzed according to the vaccination group a participant actually received.

#### Solicited Safety Set (Booster/Third Dose Analysis)

The Solicited Safety Set for Booster/Third Dose Analysis consists of all participants who received booster/third dose, and contribute any solicited AR data, i.e., have at least one post-booster/post-third solicited safety assessment in booster/third dose phase. The Solicited Safety Set will be used for the analyses of solicited ARs in Booster/Third Dose analysis.

Participants will be analyzed according to their treatment groups (mRNA-1273-mRNA-1273 Booster or Placebo-mRNA-1273-mRNA-1273 Booster for booster dose analysis and mRNA-1273-Third Dose for third dose analysis).

